8.0 CORRELATIVE STUDIES SAMPLE COLLECTIONS

Bone marrow samples will be collected pre-study, on Cycle 1 Day 10 ± 1 , and on Day 28 ± 4 of Cycle 1, 2, 4, and 6 for correlative studies. Following Cycle 6, bone marrow biopsies should be performed at the discretion of the treating physician to assess for relapse or progression. The bone marrow samples will be collected under HRPO# 201011766 (“Tissue Acquisition for Analysis of Genetic Progression Factors in Hematologic Diseases”) that all patients will be concurrently enrolled in.

Skin biopsy sample will be collected as part of the patient’s participation in HRPO# 201011766 (“Tissue Acquisition for Analysis of Genetic Progression Factors in Hematologic Malignancies”). There is no required time frame for this sample, and it may have been collected months or even years prior to the first dose of decitabine.

Peripheral blood sample (3 mL) will be collected on Cycle 1 Day 4 ± 1 . Sample must be obtained 45 minutes \pm 15 minutes after beginning the infusion, before the decitabine infusion is complete, and should be obtained from the opposite arm as the infusion. The sample should be collected in a 3 mL K3EDTA tube pre-loaded with 8 mL of tetrahydrouridine (THU 500 mcg/mL), an inhibitor of cytidine deaminase. The sample should be processed by the Tissue Procurement Core Facility at the Siteman Cancer Center. Plasma should be separated and stored per protocols.

9.0 EFFICACY, SAFETY AND CORRELATIVE STUDY MEASURES

A secondary endpoint of this study is to estimate morphologic complete remission rate.

9.1 Response Criteria - AML

AML Patients will be assessed for response according to the IWG criteria:¹

Morphologic complete remission (CR) – Defined as morphologic leukemia-free state, defined as less than 5% blasts in aspirate with marrow spicules and a count of ≥ 200 nucleated cells and no blasts with Auer rods or any persistence of extramedullary disease. When erythroid precursors constitute less than 50% of bone marrow nucleated cells, the percentage of blasts is based on all nucleated cells; when there are 50% or more erythroid cells, the percentage blasts should be based on the nonerythroid cells. The presence of mild megaloblastoid changes may be permitted if they are thought to be consistent with treatment effect. However, persistence of pretreatment abnormalities (eg, pseudo-Pelger-Hüet cells, ringed sideroblasts, dysplastic megakaryocytes) are not consistent with CR. In addition, ANC $> 1000/\mu\text{l}$ and platelet count of $\geq 100,000/\mu\text{l}$. Patient must be independent of transfusions. No duration requirement for this designation.

Cytogenetic complete remission (CCR) – Defined as morphologic complete remission plus a reversion to a normal karyotype. For this study, reversion of a normal karyotype is defined as no clonal abnormalities detected in a minimum of 20 mitotic cells.

Morphologic complete remission with incomplete blood count recovery (CRi) – Defined as morphologic complete recovery with the exception of neutropenia $< 1000/\mu\text{l}$ or thrombocytopenia $< 100,000/\mu\text{l}$.

Partial remission (PR) – Defined as meeting the above criteria for complete remission, with the following exceptions: decrease of $\geq 50\%$ in the percentage of blast to 5-25% in the bone marrow aspirate. A value of $\leq 5\%$ blasts in bone marrow with Auer rods present may also be considered a partial remission.

Stable Disease (SD) – Defined as not meeting the definitions of CR, CRi, PR, PD, or recurrence/morphologic relapse.

Progressive disease (PD) – Defined as a clear increase in bone marrow blast count, typically a greater than 50% increase compared with baseline, or new extramedullary disease. Patients with a $> 50\%$ increase in peripheral blast count with an increase of the total peripheral white blood cell count to $> 10,000/\mu\text{l}$ should undergo evaluation by bone marrow biopsy to access for progressive disease.

Recurrence/morphologic relapse - Defined as relapse following complete remission is defined as reappearance of blasts in the blood or the finding of $\geq 5\%$ blasts in the bone marrow, not attributable to any other cause. New dysplastic changes is considered

relapse. If there are no blasts in the peripheral blood and 5-20% blasts in the bone marrow, bone marrow biopsy should be repeated in > 1 week to confirm relapse.

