Patients with progressive disease after two cycles (defined as a clear increase in bone marrow blast count, typically a > 50% increase in bone marrow blasts over baseline) should be removed from study.

Patients with stable disease may continue on study and should undergo a diagnostic bone marrow biopsy at the end of even numbered cycles.

Once AML patients achieve morphologic complete remission with incomplete blood count recovery (CRi) or MDS patients achieve a marrow complete response (Marrow CR) as defined in Section 9.0, decitabine administration may be decreased to 20 mg/m²/day for ten consecutive days every 6 weeks, to limit myelosuppressive toxicity and improve count recovery. After 2 cycles at 6 week intervals, the dose may be reduce to 20 mg/m²/day for five consecutive days in 6 week cycles, at the discretion of the treating physician. After two cycles of five consecutive days of treatment, if the patient meets the definition of CR with complete cytogenetic response as defined in Section 9.0, administration may further be decreased to three consecutive days per cycle at the discretion of the treating physician.

Sample collection for correlative studies:

Bone marrow biopsies should be performed at baseline, at Cycle 1 Day 10 ± 1, and at Day 28 ± 4 of Cycles 1, 2, 4, and 6. Following Cycle 6, bone marrow biopsies should be performed at the discretion of the treating physician to assess for relapse or progression.

Peripheral blood samples should be collected on Day 4± 1 of Cycle 1. Collection should be obtained 45 ± 15 minutes after decitabine infusion is initiated.

Genomic Predictors of Decitabine Response in AML/MDS

Table of Contents

Section	Page
Section 4.21.0 INTRODUCTION	7
1.1 Rationale.....	7
1.2 Decitabine and Hypomethylating agents in AML/MDS.....	9
1.2.1 Pharmacokinetics and Metabolism of Decitabine.....	11
1.2.2 Experience with extended dosing schedules.....	12
1.3 Correlative Studies	13
2.0 OBJECTIVES.....	15
2.1 Primary Objective.....	15
2.2 Secondary Objectives	15
3.0 PATIENT SELECTION.....	16
3.1 Inclusion Criteria	16
3.2 Exclusion Criteria.....	16
3.3 Inclusion of Women and Minorities.....	17
4.0 REGISTRATION PROCEDURES	18
4.1 Confirmation of Patient Eligibility.....	18
4.2 Patient Registration in the Siteman Cancer Center Database.....	18
4.3 Assignment of UPN.....	18
5.0 INVESTIGATIONAL PLAN	20
5.1 Summary of Study Design.....	20
5.2 Study Procedures	20
5.2.1 Pre-study Procedures.....	20
5.2.2 Baseline Evaluation.....	21

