1.3 Correlative Studies

With exception of the peripheral blood sample collected on Cycle 1 Day 4, all correlative studies will be collected under HRPO# 201011766 (“Tissue Acquisition for Analysis of Genetic Progression Factors in Hematologic Diseases”) that all patients will be concurrently enrolled in. The goals of the correlative studies include:

1. To correlate patient-specific mutations with response to decitabine.
We will perform exome sequencing of each patient’s pre-study bone marrow sample and skin sample. We will determine AML/MDS-associated variants found in the bone marrow, but not skin sample. We will correlate the presence of mutations with response (especially mutations in *DNMT3A*, *IDH1*, *IDH2*, and *TET2*). This study is powered to identify mutations with >80% sensitivity to predict decitabine response if used as a clinical assay.
2. To correlate the velocity and depth of response with response to decitabine.
We will assess tumor burden by allele frequency of patient-specific mutations in bone marrow samples collected pre study, Cycle 1 Day 10±1, Cycle 1 Day 28±4, and Cycle 2 Day 28±4. We will assess mutations in at least 24 recurrently mutated genes (including, but not limited to: *FLT3*, *DNMT3A*, *NPM1*, *TET2*, *WT1*, *IDH1*, *IDH2*, *RUNX1*, *NRAS*, *TP53*, *U2AF1*, *KRAS*, *PHF6*, *MSTP9*, *PTPN11*, *KIT*, *SMC3*, *PRUNE2*, *ETV6*, *CEBPA*, *SMC1A*, *ASXL1*, *STAG2*, *RAD21*) as well as all patient-

specific mutations discovered during exome sequencing. The leukemic allele frequency will be measured using the Illumina MySeq or HiSeq platform using DNA capture by gene specific biotinylated-oligonucleotides. Patient bone marrow samples will be assessed pre-study, Cycle 1 Day 10 \pm 1, Cycle 1 Day 28 \pm 4, and Cycle 2 Day 28 \pm 4 and compared with patient specific skin samples (normal control). The velocity of response will be calculated as the natural log rate of patient-specific mutation allele frequency clearance. Depth of response will be defined as the lowest patient-specific mutation allele frequency in a bone marrow sample. The velocity and depth of tumor response will be correlated to:

- Achievement of clinical CR,
- Time to best response,
- Mutational status,
- Time to disease progression.

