9.2 Response Criteria - MDS

MDS Patients will be assessed for response according to the IWG criteria:⁶⁹

Complete remission (CR) – Defined as $\leq 5\%$ myeloblasts with normal maturation of all cell lines in the bone marrow and peripheral blood values of Hgb ≥ 11 g/dL, Platelets $\geq 100 \times 10^9/L$, Neutrophils $\geq 1.0 \times 10^9/L$, and 0% blasts. Persistent dysplasia does not exclude CR but will be noted.

Marrow Complete Response (Marrow CR) – Defined as $\leq 5\%$ myeloblasts in the bone marrow and a decrease by $\geq 50\%$ from pretreatment values, but not meeting the definition of CR above.

Partial Remission (PR) – Defined as meeting the definition of CR above with a decrease of myeloblasts in the bone marrow by $\geq 50\%$ from pretreatment values, but absolute myeloblasts still $>5\%$.

Stable Disease (SD) – Defined as not meeting the definitions of CR, Marrow CR, PR, SD, PD, or recurrence/morphologic relapse.

Progressive Disease//Relapse (PD) – Defined as $\geq 50\%$ increase in blasts to $> 5\%$ blasts (for patients with less than 5% blasts at baseline only), $\geq 50\%$ increase to $> 10\%$ blasts (for patients with 5-10% blasts at baseline only), $\geq 50\%$ increase to $> 20\%$ blasts (for patients with 10-20% blasts at baseline only), $\geq 50\%$ increase to $> 30\%$ blasts (for patients with 20-30% blasts at baseline only) or any of the following: At least 50% decrement from maximum remission/response in granulocytes or platelets, reduction in Hgb by ≥ 2 g/dL, or New or worsened transfusion dependence not related to study drug toxicity. Or for patients with a CR, Marrow CR, or PR as defined above and subsequently development of one of the following: Return to pretreatment bone marrow blast percentage, decrement of $\geq 50\%$ from maximum remission/response levels in granulocytes or platelets, or reduction in Hgb concentration by ≥ 1.5 g/dL or transfusion dependence.

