9.4 Other Secondary Efficacy Measures

9.4.1 Treatment Failure, Overall Survival and Event-free Survival

Treatment failure is defined as failure to achieve a complete or partial remission following 4 cycles of therapy.

Overall survival is defined as the date of first dose of study drug to the date of death from any cause. Patients still alive at the time of the final analysis will be right-censored.

Event-free survival is defined as the interval from the date of first dose of study drug to date of treatment failure, recurrence, death due to any cause, or loss to follow up.

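### Section 9.1 has no rule for losing an AML partial remission, so blasts that return to the pretreatment level score as stable disease

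*Combined protocol and SAP*

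**What the plan says.** - **AML progression (9.1):** "Defined as a clear increase in bone marrow blast count, typically a greater than 50% increase compared with baseline"; new extramedullary disease also qualifies. The study schema uses the same reference point: "typically a > 50% increase in bone marrow blasts over baseline".
- **AML partial remission (9.1):** blasts fall by at least half, to 5-25%, with the other remission criteria met.
- **AML recurrence (9.1):** "Defined as relapse following complete remission is defined as reappearance of blasts in the blood", or marrow blasts of 5% or more. It is defined only for patients who were in complete remission.
- **AML stable disease (9.1):** "Defined as not meeting the definitions of CR, CRi, PR, PD, or recurrence/morphologic relapse". This is the residual category.
- **MDS progression/relapse (9.2):** a clause opens "Or for patients with a CR, Marrow CR, or PR as defined above and subsequently development of one of the following", and its first item is marrow blasts back at the pretreatment percentage. Section 9.1 has no counterpart.
- **Use of these categories:** Section 1.3 correlates velocity and depth of mutation clearance with "Time to disease progression". Section 9.4 does not define that endpoint separately, so the categories in 9.1 and 9.2 have to supply its events. Event-free survival (EFS, 9.4.1) runs from first dose "to date of treatment failure, recurrence, death due to any cause, or loss to follow up". Progression is not on that list. Treatment failure means not having achieved complete or partial remission after four cycles.

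**The concern.** A PR counts as a response in Section 14.2.3, so losing one should end the response in the time-to-event data. For AML it need not. A patient in complete remission has an EFS recurrence event once marrow blasts are back at 5%, subject to the repeat-biopsy rule in 9.1. A patient in PR whose leukemia returns in full has no EFS event until death or loss to follow-up. That patient also has no progression event until blasts clearly exceed the pretreatment level or extramedullary disease appears.

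The weaker response can therefore be given the longer time. AML and MDS patients, whom Section 1.1 says will be analysed together, are also scored differently for the same marrow course.

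**Working it through.** The plan states no figure on this point, so there is nothing to reproduce. The check applies the definitions to the possible blast values.

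**Inputs.** Let b be baseline marrow blasts (%). PR requires a fall of at least 50% to 5-25%; the progression guide is a rise of more than 50% over b (both 9.1). Blasts cannot exceed 100%. Section 3.1 sets a lower limit on disease burden (above 10%) but no upper limit on marrow blasts.

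**Formulas.**
- Upper edge of PR: U = min(25, b/2).
- Numeric progression guide: blasts > 1.5 x b.
- Values that are neither PR, recurrence nor progression on the guide: above U, up to min(100, 1.5 x b).

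| b | U | guide (>1.5b) | scored SD after losing PR | top of gap / U |
|---|---|---|---|---|
| 20 | 10 | >30 | >10 to 30 | 3.0 |
| 40 | 20 | >60 | >20 to 60 | 3.0 |
| 60 | 25 | >90 | >25 to 90 | 3.6 |
| 66 | 25 | >99 | >25 to 99 | 4.0 |
| 70 | 25 | >105 (unreachable) | >25 to 100 | 4.0 |

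The gap has two parts. From U up to b there is no increase over baseline at all, so no reading of a clear increase over baseline makes it progression. From b up to 1.5 x b the guide is not met, and the call is left to judgement.

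**Worked record.** Baseline 40%; PR at 15%, still held at the Cycle 4 marrow; 40% at the Cycle 6 marrow; no new extramedullary disease.
1. PR is valid: (40 - 15)/40 = 62.5% fall, and 15% lies within 5-25%.
2. Progression at Cycle 6: (40 - 40)/40 = 0% rise, so no.
3. Recurrence: no prior complete remission, so no.
4. Treatment failure: PR was achieved and held through four cycles, so no.
5. What remains is stable disease, with no progression event and no EFS event.
6. The same blast course in MDS, after an MDS PR, is progression/relapse under 9.2.

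**Where the guide stops working.** 1.5 x b reaches 100% at b = 100/1.5 = 66.7%. From there upward the guide cannot be met, and marrow progression rests on judging a clear increase.

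**CRi.** Section 9.1 lists CRi separately from CR, so its status under recurrence and treatment failure has to be inferred. If CRi is complete remission, blasts of 5% or more are a recurrence and an EFS event. If it is not, a patient whose best response is CRi has not reached complete or partial remission after four cycles; that is treatment failure, also an EFS event. EFS records an event on either reading, but its date and the event for time to progression depend on which is meant.

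**The case against.** The strongest reply is that the progression rule is not purely numeric. The full wording is a clear increase, "typically a greater than 50% increase compared with baseline, or new extramedullary disease", so 50% is a guide and there is a second route. This stands, and it rules out some stronger readings:

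- A reader might infer that only a rise above 50% counts, or that every lost PR is scored stable. Neither is so: blasts above 1.5 x baseline, a smaller rise judged clear, or new extramedullary disease is progression.
- A reader might infer that patients entering with two-thirds blasts or more cannot progress. They cannot meet the guide, but an assessor may still call 75% rising to 95% a clear increase.
- A reader might infer that a CRi patient who relapses has no EFS event until death. The two readings above show otherwise.

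The latitude does not rescue the worked record, because blasts equal to baseline are not an increase over baseline, and 9.1 and the schema name no other reference point.

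It is also fair that AML and MDS follow separately cited response criteria, so different rules are not in themselves a fault. The difficulty is that the AML rule leaves a returned leukemia labelled stable. The consequence is limited: time to progression is one correlative item with no analysis described for it in Section 14, and Section 14.2.3 only lists relapse and death times by patient.

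**Conclusion.** The gap is real and follows from the current text without any distributional assumption. After an AML PR, blasts can return to the pretreatment level, and on the 50% guide to as much as 1.5 times it, and still be stable disease. That top value is 3 to 4 times the upper edge of the PR range in the cases tabulated.

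It affects time to disease progression and EFS. It does not affect the primary mutation-response test, which depends on whether a response was reached. The comparison with complete-remission patients on time to progression assumes that recurrence counts as a progression event there, which the plan does not state.

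No patient count can be given. The documents contain neither a baseline blast distribution nor an expected number of AML PRs or of PR losses, and any percentage of patients above two-thirds blasts or in CRi would rest on invented distributions.

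**What to change.** For endpoint scoring only, amend Section 9.1 as follows.
1. Under recurrence, add that marrow blasts back at the pretreatment percentage after an AML PR are an event, on the model of 9.2, and that this counts for time to disease progression. Placed there, it reaches EFS without changing the event list in 9.4.1.
2. State that CRi counts as complete remission in the recurrence and treatment-failure definitions, consistent with the CR/CRi grouping in 14.2.3.
3. Keep the marrow clear-increase route for baseline blasts of 66.7% or more, and note that the 50% guide cannot be reached there. Do not substitute the peripheral-blast and white-count rule: 9.1 uses it to trigger a marrow examination, not as evidence of progression.

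The cost is a few sentences, using marrow data already collected. Some AML event times become earlier. Blasts above the PR range but below the pretreatment level would still be stable disease, as under the 9.2 clause.

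The schema and Section 5.3 use progression for removal from study and for ending therapy. Those passages should be reconciled separately with the amended definitions; no treatment rule is proposed here.

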9.2 Response Criteria - MDS

MDS Patients will be assessed for response according to the IWG criteria:⁶⁹

Complete remission (CR) – Defined as $\leq 5\%$ myeloblasts with normal maturation of all cell lines in the bone marrow and peripheral blood values of Hgb ≥ 11 g/dL, Platelets $\geq 100 \times 10^9/L$, Neutrophils $\geq 1.0 \times 10^9/L$, and 0% blasts. Persistent dysplasia does not exclude CR but will be noted.

Marrow Complete Response (Marrow CR) – Defined as $\leq 5\%$ myeloblasts in the bone marrow and a decrease by $\geq 50\%$ from pretreatment values, but not meeting the definition of CR above.

Partial Remission (PR) – Defined as meeting the definition of CR above with a decrease of myeloblasts in the bone marrow by $\geq 50\%$ from pretreatment values, but absolute myeloblasts still $>5\%$.

Stable Disease (SD) – Defined as not meeting the definitions of CR, Marrow CR, PR, SD, PD, or recurrence/morphologic relapse.

Progressive Disease//Relapse (PD) – Defined as $\geq 50\%$ increase in blasts to $> 5\%$ blasts (for patients with less than 5% blasts at baseline only), $\geq 50\%$ increase to $> 10\%$ blasts (for patients with 5-10% blasts at baseline only), $\geq 50\%$ increase to $> 20\%$ blasts (for patients with 10-20% blasts at baseline only), $\geq 50\%$ increase to $> 30\%$ blasts (for patients with 20-30% blasts at baseline only) or any of the following: At least 50% decrement from maximum remission/response in granulocytes or platelets, reduction in Hgb by ≥ 2 g/dL, or New or worsened transfusion dependence not related to study drug toxicity. Or for patients with a CR, Marrow CR, or PR as defined above and subsequently development of one of the following: Return to pretreatment bone marrow blast percentage, decrement of $\geq 50\%$ from maximum remission/response levels in granulocytes or platelets, or reduction in Hgb concentration by ≥ 1.5 g/dL or transfusion dependence.

9.2.1 Hematologic Improvement (HI)

Progressive disease as defined above nullifies hematologic improvement.

Erythroid response requires all of the following (only required if pretreatment HgB <11 g/dL):

- Hgb increase by ≥ 1.5 g/dL
- Relevant reduction of units of RBC transfusions by an absolute number of at least 4 RBC transfusions/8 wk compared with the pretreatment transfusion

number in the previous 8 wk. Only RBC transfusions given for a Hgb of ≤ 9.0 g/dL pretreatment will count in the RBC transfusion response evaluation

Platelet response requires one of the following (only required if pretreatment platelets $< 100 \times 10^9/L$):

- Absolute increase of $\geq 30 \times 10^9/L$ (for patients starting with $> 20 \times 10^9/L$ platelets)
- Increase from $< 20 \times 10^9/L$ to $> 20 \times 10^9/L$ and absolute increase $\geq 100\%$ (for patients starting with $< 20 \times 10^9/L$)

Neutrophil response requires the following (only required if pretreatment ANC $< 1.0 \times 10^9/L$):

- At least 100% increase and an absolute increase $> 0.5 \times 10^9/L$

9.3.1 Cytogenetic Response

Complete Cytogenetic Response – Defined as reversion to a normal karyotype. For this study, reversion of a normal karyotype is defined as no clonal abnormalities detected in a minimum of 20 mitotic cells. Progressive disease as defined above nullifies cytogenetic response.

9.3 Guidelines for Evaluation of Disease

Bone marrow biopsy should be performed on Day 28 ± 4 of cycles 1, 2, 4 and 6 for clinical disease assessment. Following Cycle 6, bone marrow biopsies should be performed at the discretion of the treating physician to assess for relapse or progression.

9.4 Other Secondary Efficacy Measures

9.4.1 Treatment Failure, Overall Survival and Event-free Survival

Treatment failure is defined as failure to achieve a complete or partial remission following 4 cycles of therapy.

Overall survival is defined as the date of first dose of study drug to the date of death from any cause. Patients still alive at the time of the final analysis will be right-censored.

Event-free survival is defined as the interval from the date of first dose of study drug to date of treatment failure, recurrence, death due to any cause, or loss to follow up.

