5.2.11 Post-study Follow-up

Patients are to be followed according to standard patient care procedures for 30 days following the date of the last decitabine dose to monitor for toxicity, survival, and response. Thereafter, the investigator or designee will record information on subsequent therapy, disease progression, and/or death every 6 months for 2 years after last dose of study drug or until the patient is lost to follow-up or dies.

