9.4.2 Duration of Remission and Relapse-free Survival for Patients Having Complete Remission

Duration of complete remission is defined as the interval from the date that complete remission is documented to the date of recurrence, death due to any cause, or loss to follow-up.

Relapse-free survival is defined only for those patients achieving a complete remission. It is defined as the interval from the date of first documentation of a leukemia-free state to the date of recurrence, death due to any cause, or loss to follow up.

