^h Decitabine treatment will be 20 mg/m² over a 1-hour IV infusion on consecutive Days 1-10 every 28-day cycle. The dose will be calculated based on actual patient weight at the beginning of each cycle. Patients may be premedicated with lorazepam, prochlorperazine, palonosetron, or ondansetron at the treating physician's discretion.

ⁱ Patients will be followed for 30 days following the date of the last decitabine dose to monitor for toxicity, survival and response. Thereafter, the investigator or designee will record information on subsequent therapy, disease progression, and death, every 6 months for 2 years after first dose of study drug or until the patient is lost to follow-up.

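### EFS, relapse-free survival and remission duration list loss to follow-up as an end point with no censoring rule, and EFS omits progression, so an AML patient removed early for progression can have longer EFS than one with stable disease

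*Combined protocol and SAP*

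**What the plan says.** References are to the protocol version whose statistical chapter is Section 14.

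- **EFS (9.4.1)** runs from first dose "to date of treatment failure, recurrence, death due to any cause, or loss to follow up".
- **Treatment failure (9.4.1):** "Treatment failure is defined as failure to achieve a complete or partial remission following 4 cycles of therapy". No class or date is given for a patient who stops sooner.
- **Relapse-free survival (9.4.2)** runs from first documentation of a "leukemia-free state to the date of recurrence, death due to any cause, or loss to follow up". **Remission duration (9.4.2)** runs from the date that "complete remission is documented to the date of recurrence, death due to any cause, or loss to follow-up".
- **Censoring** is mentioned once, for overall survival (9.4.1): "Patients still alive at the time of the final analysis will be right-censored".
- **Progression:** under the Study Schema, "Patients with progressive disease after two cycles" come off study, while stable disease may continue. Section 5.3 makes confirmed progression a reason to end treatment at any time.
- **Recurrence:** Section 9.1 (AML) limits it to relapse after complete remission and defines progressive disease separately. Section 9.2 (MDS) puts progression and relapse under one combined label.
- **Length of follow-up:** Section 5.2.11 has data recorded "every 6 months for 2 years after last dose of study drug", and the Follow Up Form entry in Section 15 agrees. Footnote i of the Appendix 2 flow chart says "every 6 months for 2 years after first dose of study drug".
- **Use in the analysis:** Section 14 contains no EFS, relapse-free survival or remission-duration analysis. Times to relapse and death are to be listed per patient (14.2.3), and the subgroup section (14.2.5) names only the primary and overall survival endpoints.

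**The concern.** Two features of the definitions go wrong if they are followed as written.

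First, loss to follow-up stands in the same list as relapse and death. For overall survival the protocol says who is censored; for the other three measures it does not. An analyst who takes the lists at face value codes a lost patient as a failure. Another who treats the loss date as the last observation codes the same patient as censored.

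Second, the EFS list has no entry for a patient whose disease progresses without ever remitting. In AML such a patient cannot have a recurrence, and once removed after two cycles does not reach the four-cycle test. The patient with the worse course may then carry the longer EFS. Others who stop before Cycle 4 for toxicity, withdrawal or lack of response fall into the same gap.

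Separately, the two stated ends of follow-up give different observation windows for every time-to-event measure.

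At stake is whether any EFS, relapse-free survival or remission-duration figure from this trial can be interpreted, or set beside published figures. With nothing on them in Section 14, Section 9.4 is the only text that controls how they are calculated.

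**Working it through.** The plan gives no event count, rate or power for these three measures, so there is no figure to reproduce. The check applies the definitions to the protocol's own timeline.

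**1. Timeline.** Cycles are 28 days (5.1) and marrow assessments fall on Day 28 ± 4 of Cycles 1, 2, 4 and 6 (9.3).
- End of Cycle 2: 2 × 28 = day 56 (52 to 60).
- End of Cycle 4: 4 × 28 = day 112 (108 to 116).

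**2. Literal EFS.**
- Stable disease, continuing, no remission after four cycles: treatment failure at about day 112.
- AML, removed for progression at about day 56: no recurrence, because there was no remission; no treatment failure, because four cycles were not given. EFS runs on to death or loss.

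Take one such AML patient who dies on day 180 (illustrative). EFS is 180 days on the literal reading, 112 if early stoppers are failed at the four-cycle point, and 56 if they are failed at removal. The text does not choose among these.

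**3. How often the order could reverse.** It reverses only if the patient is alive and followed past about day 112. Assume exponential survival after removal with median m months, no loss before day 112, and 30.4375 days per month:

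P(EFS > 112 days) = exp(−ln 2 × t / m), with t = (112 − day of removal) / 30.4375.

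For removal at day 56, t = 56 / 30.4375 = 1.84 months. For progression at day 28, t = 84 / 30.4375 = 2.76 months.

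| Assumed median m (months) | 1 | 2 | 3 | 4 | 6 | 12 |
|---|---|---|---|---|---|---|
| Removal at day 56 | 28% | 53% | 65% | 73% | 81% | 90% |
| Progression at day 28 | 15% | 38% | 53% | 62% | 73% | 85% |

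Survival after removal is not given in the documents, so the whole range is shown. If progression were an EFS event, the day-56 patient would have EFS of 52 to 60 days against 108 to 116 for stable disease, and the order would always be progression first.

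**4. Loss counted as an event.** With constant event hazard h and loss hazard c, the median is ln 2 / h if losses are censored and ln 2 / (h + c) if they are counted. The ratio is h / (h + c) = 1 − f, where f = c / (h + c) is the share of intervals ending in loss. For assumed f of 5%, 10% and 20% the ratio is 0.95, 0.90 and 0.80. This fixes the direction (shorter times); the size depends on f, which the documents do not give.

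**5. Follow-up window.** For a patient treated for 18 months (illustrative), Section 5.2.11 gives 24 months of follow-up after treatment. Footnote i gives 24 − 18 = 6 months.

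**The case against.** The strongest reply is that these are unclear definitions of minor measures. Several parts of it stand.

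- **Loss to follow-up is not called an event.** The sections define intervals ending at one of several dates, and the loss date may be meant only as the end of observation. That is possible, but nothing says so, and the one explicit censoring rule is confined to overall survival.
- **Treatment failure can be read as not being in remission by the four-cycle point.** A patient removed for progression then also fails and the reversal disappears. This is a fair reading, but no rule or date for early stoppers supports it over the literal one.
- **MDS differs from AML.** Under the combined label in Section 9.2, recurrence might include progression, although the stable-disease definition there still lists the two separately. The omission is clear only for AML.
- **Day 112 is nominal.** Section 6.1 holds treatment for infection, and Section 6.0 ends participation only when the gap between cycles exceeds 8 weeks.

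A reader might infer three stronger claims that the documents do not support. One is that early progressors as a group get longer EFS: this fails for anyone who dies or is lost before about day 112. Another is that medians are shortened by 10% to 20%. No loss share is stated for these measures; the 20% drop-out figure in Section 14.2.2 concerns molecular evaluability. Constant hazards also sit badly with failures clustered near day 112 when Section 14.2.3 assumes 55 non-responders in 100, so the EFS median may lie near that cluster however losses are coded. The third is that comparisons by mutation or response are distorted: Section 14 plans none on these measures.

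**Conclusion.** The point holds in limited form. As written, Sections 9.4.1 and 9.4.2 allow loss to follow-up to be coded as failure in three measures, and leave progression out of EFS. Under the literal definitions an AML patient removed for progression at about day 56 can have longer EFS than a stable-disease patient failing at about day 112. That requires survival and follow-up past day 112, and that early stoppers are not otherwise counted as failures. The modelled frequency, 28% to 90% for removal at day 56, rests wholly on assumed median survival of 1 to 12 months and shows that the reversal may be common, not that it will be. For MDS the text is ambiguous.

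The effect is confined to other secondary measures with no planned comparison. The primary mutation–response analysis, the response rates and the definition of overall survival are not touched by the event lists. The conflict over the end of follow-up is real and separate: it sets how long patients are observed, not how events are coded.

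**What to change.** Amend the wording of Sections 9.4.1 and 9.4.2:

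1. Define the EFS event as the first of progression, treatment failure, relapse or death, and say how this applies to the combined MDS category.
2. Define treatment failure as no complete or partial remission by the four-cycle assessment, dated at that assessment. State the classification and date for patients who stop before Cycle 4 for any reason, since they may have no Cycle 4 marrow.
3. For EFS, relapse-free survival and remission duration, state that patients lost to follow-up without an event are censored. Name the date to be used (last disease assessment or last contact), and apply a matching rule to patients still event-free at the final analysis.
4. Reconcile Section 5.2.11 and Section 15 with footnote i of Appendix 2, so that one end of follow-up is stated.

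The cost is protocol and SAP wording. Items 1 to 3 need no new data: progression and death are already recorded in follow-up, and an End of Study Form is due when a patient is lost. They are analysis definitions and change no treatment rule. Item 4 may change how long some patients are followed, depending on which statement sites have been using.
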